### **g) Procedures Involved in the Human Research**

Study subjects will undergo breast surgery by the individual surgeon's standard technique. No changes in surgical technique will occur as part of this study. Regional nerve block with bupivacaine and/or lidocaine is typically offered to patients as part of this procedure and is considered standard of care. However, not all patients opt to receive a nerve block

For the study, subjects will be randomized to experimental and control groups in a ratio of 1:1. Randomization will occur upon enrollment in the study. When the patient is enrolled, the investigator will use the Sealed Envelope™ simple randomization tool to assign the subject a treatment group. Randomization occurs in random permuted blocks to achieve an even distribution between groups. Patients will be blinded to their study group.

All subjects will receive perineural nerve block in the preoperative holding area prior to the case performed by faculty from the anesthesia pain service. An ultrasound guided pecs block will be performed. For the block, the fascial plane separating the pectoralis major and pectoralis minor muscles is identified by ultrasound at the level of the 3rd rib. A needle is advanced into this space and the local anesthetic is infiltrated. The experimental group will receive 29cc 0.5% bupivacaine mixed with 1mL 4mg/mL dexamethasone for each side (40 cc total). The control group will receive 29cc 0.5% bupivacaine mixed with 1mL 0.9% saline solution for each side.

All patients will undergo standard breast reduction with no change in the standard operative technique.

All patients will receive a standard postoperative pain regimen as follows:

- Percocet 5/325 1 tab q4hr prn pain (moderate, 4 – 7)
- Percocet 5/325 2 tabs q4hr prn pain (severe, 8 – 10)
- IV 1mg Morphine q1hr prn breakthrough pain
- IV 4mg Zofran q8hrs prn N/V

This may be adjusted for patient drug allergies

Bupivacaine is a local analgesic used routinely during surgical procedures. It is FDA approved for this indication.

Dexamethasone is a glucocorticoid available in oral and intravenous formulations. It is FDA approved for a multitude of anti-inflammatory indications. While off label, it is standard of care to provide IV

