## Enhanced pain control after reduction mammoplasty with bupivacaine and dexamethasone regional block

### 1) Abstract of the study

**Background:** Patients undergoing reduction mammoplasty frequently suffer significant post procedure pain at the operative site. While regional nerve block is routinely performed with bupivacaine, the effects of this are limited to the up to 8 hours of action provided by this drug. Previous studies in orthopedic and thoracic surgery patients have demonstrated that addition of dexamethasone to the perineural block prolongs the duration of analgesia. This has never been studied in the plastic surgery patient. We propose that addition of dexamethasone to the infiltration solution will prolong the duration of analgesia provided by a regional block and reduce the need for adjunct narcotic medication in the postoperative period following reduction mammoplasty.

**Methods:** Patients undergoing elective Breast Surgery at Temple University Hospital will be randomized to receive a control standard perineural block with 19-mL 0.5% bupivacaine +1mL 0.9% sterile saline or block with the experimental mixture of 19mL 0.5% bupivacaine + 1mL 4mg/mL dexamethasone solution for each breast. Primary end points will be mean pain VAS score as measured every 4 hours postoperatively and postoperative narcotic consumption data during the admission following the procedure. Secondary endpoints also observed will be anti-emetic consumption, vital signs, quality of life as assessed by SF-36 and Breast-Q questionnaires, and length of hospital stay.

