### **b) Inclusion and Exclusion Criteria**

Initial in office screening will easily identify all patients who are requesting and scheduling breast reduction surgery. Criteria to be included in the study are women aged 18-80 undergoing elective bilateral breast surgery with ASA class 1-3.

Exclusion criteria are allergy to any of the study medications, history of chronic pain condition or narcotic dependency, history of chronic renal or hepatic disease, history of diabetes mellitus, and history of previous post operative nausea and vomiting. Prisoners and pregnant patients will also be excluded. Screening for appropriate subjects will occur in the clinic. ASA determination will be made by the anesthesia department during preoperative testing.

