## Enhanced pain control after reduction mammoplasty with bupivacaine and dexamethasone regional block

dexamethasone to prevent post-operative nausea and vomiting. It has not been evaluated by the FDA as an adjunct to local anesthesia.

Pain VAS scores are routinely collected by nursing staff and entered into Epic. We will request pain evaluations at 4 hour intervals for study patients following surgery which will be entered into the Epic medical record. Medication administration is also captured in the electronic medical record. Study data will be gathered from the Epic electronic medical record.

Patients will be asked to complete the MD Anderson Brief Pain Inventory Short Form and both the Breast-Q or the SF-36 questionnaire at their first post-operative visit.

As previously stated, regional block with bupivacaine alone is routinely offered and provided to patients. Patients who do not consent to participate in the study will be offered a regional nerve block containing only bupivacaine. Anesthesia pain service faculty will perform the block regardless of study participation or study group.

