### **h) Data and Specimen Banking**

Data will be collected and stored in an electronic database stored on the encrypted hospital network. All data will be stored in a password protected and encrypted manner.

Identifying patient information including name, date of birth, and medical record number and the associated study ID will be stored in a password protected document accessible only to the PI and study coordinator.

A separate database containing the de-identified study ID number and all collected study data will also be stored in a password protected, encrypted file. This file will contain clinical information such as pain scores, narcotic use, and length of stay. This database will be accessible to all study personnel involved in administering the study.

The database containing identifying patient information will be destroyed upon completion of all data analyses. All patient medical records will be cleared of the study ID at this time. The deidentified database will be maintained indefinitely for potential ongoing analysis.

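### The study block is specified at two different volumes: 30 mL per side (60 mL, 290 mg bupivacaine per patient) or 20 mL per side (40 mL, 190 mg)

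*Combined protocol and SAP*

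**What the plan says.** Two places in the protocol give the composition of the block.

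- **Section 10(g), Procedures, experimental arm:** "The experimental group will receive 29cc 0.5% bupivacaine mixed with 1mL 4mg/mL dexamethasone for each side (40 cc total").
- **Section 10(g), control arm:** "The control group will receive 29cc 0.5% bupivacaine mixed with 1mL 0.9% saline solution for each side". No total is given for this arm.
- **Section 1, Abstract, experimental arm:** "block with the experimental mixture of 19mL 0.5% bupivacaine + 1mL 4mg/mL dexamethasone solution for each breast".
- **Section 1, Abstract, control arm:** "control standard perineural block with 19-mL 0.5% bupivacaine +1mL 0.9% sterile saline", on the same per-breast basis.

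Section 10(b) fixes the number of sides at two, because it admits only "women aged 18-80 undergoing elective bilateral breast surgery with ASA class 1-3".

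**The concern.** Section 10(g) is where the staff performing the block would look for the dose. Its per-side volume and its total cannot both be followed, and its per-side volume disagrees with the abstract by 10 mL of bupivacaine.

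The trial asks whether an additive prolongs a bupivacaine block, so the base block ought to be fixed. Faculty of the anesthesia pain service perform the blocks, and different operators could reasonably act on different figures. The 40 cc total is attached only to the experimental sentence. A reader who took each sentence separately could give 40 mL in one arm and 60 mL in the other. Section 13 says that allocation is disclosed to the staff caring for the patient, so blinding would not prevent this. The documents do not show that it happened, but it is a route by which an ambiguous instruction could become a difference between arms.

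Section 11 lists inadvertent systemic injection of the anesthetic among the risks, and that risk cannot be weighed against a dose that is uncertain by about half. Nor could a report state the intended block from this protocol.

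**Working it through.** **Inputs**

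- Section 10(g): 29 mL of 0.5% bupivacaine plus 1 mL additive per side, both arms; stated total 40 cc (experimental arm only).
- Abstract: 19 mL of 0.5% bupivacaine plus 1 mL additive per breast, both arms.
- Section 10(b): bilateral surgery, so 2 sides.
- 0.5% bupivacaine = 5 mg/mL. Dexamethasone: 1 mL of 4 mg/mL per side.

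**Step 1: try to reproduce the stated total**

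Total volume = 2 × (bupivacaine mL + 1 mL additive).

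- From 10(g): 2 × (29 + 1) = 60 mL. The stated 40 cc is not reproduced.
- Other readings of 10(g): one side only, 29 + 1 = 30 mL; bupivacaine alone on both sides, 2 × 29 = 58 mL. Neither gives 40.
- From the abstract: 2 × (19 + 1) = 40 mL. This matches.

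**Step 2: convert to dose**

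Bupivacaine per side = mL × 5 mg/mL, doubled for the patient. Dexamethasone per patient = 2 × 1 mL × 4 mg/mL.

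| | 19 + 1 mL (abstract) | 29 + 1 mL (10(g)) |
|---|---|---|
| Volume per side | 20 mL | 30 mL |
| Volume per patient | 40 mL | 60 mL |
| Bupivacaine per side | 19 × 5 = 95 mg | 29 × 5 = 145 mg |
| Bupivacaine per patient | 190 mg | 290 mg |
| Bupivacaine concentration | 95/20 = 4.75 mg/mL | 145/30 = 4.83 mg/mL |
| Dexamethasone per patient | 8 mg | 8 mg |
| Dexamethasone concentration | 4/20 = 0.20 mg/mL | 4/30 = 0.133 mg/mL |

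**Step 3: size of the conflict**

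- Bupivacaine: 290 − 190 = 100 mg per patient; 100/190 = 52.6%.
- Volume: 60 − 40 = 20 mL per patient; 20/40 = 50%.
- The bupivacaine concentration barely changes (4.83/4.75 = 1.018), so the conflict is one of volume and total dose, not strength.

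The 40 cc figure states a volume only. The 190 mg follows from it once 1 mL of additive per side is subtracted: (40 − 2) × 5 = 190 mg. It also follows directly from the abstract.

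**The case against.** The strongest reply is that the evidence is not evenly divided. Both arms of the abstract and the 40 cc total fit 19 mL, and only the 29 in 10(g) points the other way. It may be a typing error carried across two parallel sentences. That is the likelier reading, but it is not certain. The 29 appears in both arm sentences, and the volume could equally have been raised there without the abstract and the total being updated. No change history in the available text decides between these.

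A second reply is that little follows for the comparison, and most of this stands. Each section gives the two arms equal per-side volumes, so no imbalance is planned. The dexamethasone dose is the same under both versions. The power calculation in section 10(i) does not use block volume. If operators followed different versions without regard to arm, the expected result is added variability rather than bias. The documents give no maximum bupivacaine dose and no patient weights, so no safety breach can be claimed.

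A third reply is that the report could describe what was given, since 10(g) says: "Medication administration is also captured in the electronic medical record". This is partly right, but the sentence does not say that the block volume itself is recorded, and a record of what was given does not tell staff what to give.

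**Conclusion.** The concern holds. Section 10(g) as written implies 60 mL and 290 mg of bupivacaine per patient, while its own total and the abstract imply 40 mL and 190 mg. The gap is 20 mL and 100 mg per patient.

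This rests on three things: two sides per patient, as eligibility requires; the usual meaning of 0.5% as 5 mg/mL; and the absence of any reconciling statement. The last can be asserted only for the text available, because two parts of the document were not.

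The correction is essential because this is the operative dosing instruction for the study block. That judgement does not depend on any demonstrated bias or harm. If one version is used throughout in both arms, the randomised comparison is not biased by this conflict.

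**What to change.** The sponsor should confirm the intended volume and make every statement of it agree.

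- **If 19 mL is intended**, as the abstract and the 40 cc total suggest: change 29 to 19 mL in both arm sentences of 10(g) and keep 40 mL as the total.
- **If 29 mL is intended**: change both arms in the abstract to 29 mL and the total in 10(g) to 60 mL.
- **Either way**: state per-side and total mL, and bupivacaine mg, in the same form for both arms, so that only the 1 mL additive differs. Give the control arm a total as well.

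If patients have already been treated, add the block volume given to the medical-record extraction and report it by arm. First check that the record holds it. This has to be done while records can still be linked to study IDs. Section 10(h) says: "The database containing identifying patient information will be destroyed upon completion of all data analyses", and the study IDs are cleared from the medical records at the same time.

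The cost is a short protocol correction, touching two or three statements and submitted to the IRB, plus one extra data field if treatment has begun. The sample size and the analysis do not change.

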## Enhanced pain control after reduction mammoplasty with bupivacaine and dexamethasone regional block

dexamethasone to prevent post-operative nausea and vomiting. It has not been evaluated by the FDA as an adjunct to local anesthesia.

Pain VAS scores are routinely collected by nursing staff and entered into Epic. We will request pain evaluations at 4 hour intervals for study patients following surgery which will be entered into the Epic medical record. Medication administration is also captured in the electronic medical record. Study data will be gathered from the Epic electronic medical record.

Patients will be asked to complete the MD Anderson Brief Pain Inventory Short Form and both the Breast-Q or the SF-36 questionnaire at their first post-operative visit.

As previously stated, regional block with bupivacaine alone is routinely offered and provided to patients. Patients who do not consent to participate in the study will be offered a regional nerve block containing only bupivacaine. Anesthesia pain service faculty will perform the block regardless of study participation or study group.

### **h) Data and Specimen Banking**

Data will be collected and stored in an electronic database stored on the encrypted hospital network. All data will be stored in a password protected and encrypted manner.

Identifying patient information including name, date of birth, and medical record number and the associated study ID will be stored in a password protected document accessible only to the PI and study coordinator.

A separate database containing the de-identified study ID number and all collected study data will also be stored in a password protected, encrypted file. This file will contain clinical information such as pain scores, narcotic use, and length of stay. This database will be accessible to all study personnel involved in administering the study.

The database containing identifying patient information will be destroyed upon completion of all data analyses. All patient medical records will be cleared of the study ID at this time. The deidentified database will be maintained indefinitely for potential ongoing analysis.

### **i) Data Management**

Prior to data collection, patients will be randomized into 2 groups (control or experimental). An independent source will generate a master list of study IDs and associated randomization status. Patients will assigned within the master list and randomized accordingly per the master list.

## Enhanced pain control after reduction mammoplasty with bupivacaine and dexamethasone regional block

Data will be extracted from the Epic electronic medical record. Consultation with medical informatics has been obtained to assist with development of an automated data collection mechanism. Data will be stored in a spreadsheet that allows for manipulation and analysis. Patient surveys will be conducted a week after the procedure and documented on paper and the responses will be manually inputted into an electronic database (REDCap). Survey responses (REDCap) will be matched to inpatient data measurements (Epic) through study ID numbers. The spreadsheet itself will be encrypted and will be stored exclusively on hospital network databases.

The two groups will be compared using a Student T test to evaluate for significant differences in the endpoints of each group.

A 2 mean 2 sided power analysis was conducted assuming the mean VAS difference between groups to be 1.5. A sample size of 30 in each group will have 81% power to detect a difference in means of 1.500 assuming that the common standard deviation is 2.000 using a two group t-test with a 0.050 two-sided significance level. We anticipate using larger numbers to power subgroup analysis.

Analysis between the two groups will involve a linear mixed effect model to compare the pain scales of the two groups over time. If vital signs are dissimilar at the beginning of the study, they will be controlled for prior to analysis. Pain medication requirement (determined by quantity of pills or mg used of same medication) will also be controlled within the analysis model. Adjustments to the pain score within the groups due to pain medication usage will be performed.

However, need for postoperative anti-emetic therapy is expected to be a somewhat rare event with similar means. In a similar power analysis with an expected group A mean of 0.5 doses and group B mean of 1 dose with standard deviation of 1, a sample size of 63 is required to reach significance. A somewhat large standard deviation is expected given the need for repeated dosing in those who do experience post-operative nausea

Similarly, length of hospital stay is expected to be similar between the two groups. The difference is generally expected to be between a “before lunch” or “after lunch” discharge on post-operative day 1. A two-group t test with a 0.05 two-sided significance level will be used to evaluate a difference in length of hospital stay. Therefore, a 2 mean 2 sided power analysis assuming group A mean hospital stay of 16 hours and group B mean stay of 18 hours with 4 hour standard deviation, a sample size of 63 is required to achieve 80% power with  $p < 0.05$ .

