### 5) Objectives

This study aims to evaluate the effect of the addition of dexamethasone to a standard bupivacaine nerve block following reduction mammoplasty. We propose that addition of dexamethasone to the infiltration solution will prolong the duration of analgesia provided by a regional block and reduce the need for adjunct narcotic medication in the postoperative period following reduction mammoplasty.

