### **f) Study Endpoints**

Primary study endpoints are average VAS pain score during hospitalization and postoperative narcotic usage during the hospitalization. Secondary endpoints are need for antiemetic therapy, length of hospitalization, and aggregate pain and quality of

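### The mixed model for pain adjusts for post-operative narcotic use, which is itself a primary endpoint, and the plan does not say whether this model or the unadjusted t test is primary

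*Combined protocol and SAP*

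**What the plan says.** Section 10(f) sets two primary endpoints: "Primary study endpoints are average VAS pain score during hospitalization and postoperative narcotic usage during the hospitalization". Section 5 expects the added dexamethasone to "reduce the need for adjunct narcotic medication in the postoperative period following reduction mammoplasty".

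Section 10(i) then describes two analyses of pain.

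- **t test.** "The two groups will be compared using a Student T test to evaluate for significant differences in the endpoints of each group". The VAS sample size calculation (30 per arm, difference 1.5, SD 2.0, 81% power) is done "using a two group t-test with a 0.050 two-sided significance level".
- **Mixed model.** "Analysis between the two groups will involve a linear mixed effect model to compare the pain scales of the two groups over time". For this model, "Pain medication requirement (determined by quantity of pills or mg used of same medication) will also be controlled within the analysis model". The next sentence adds: "Adjustments to the pain score within the groups due to pain medication usage will be performed". No method is given for that step.

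Section 10(g) places randomisation at enrolment, before the block and surgery. It links the Percocet order to the recorded pain score, with one tablet for moderate pain and a heavier line that reads "Percocet 5/325 2 tabs q4hr prn pain (severe, 8 – 10". Intravenous morphine is available for breakthrough pain, with no score band.

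The available text does not call either analysis primary, and does not call the medication-adjusted model a sensitivity, supportive or mediation analysis.

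**The concern.** Randomisation protects a comparison of the arms on pain only as long as nothing that happens after randomisation is held fixed. By the protocol's own account, narcotic use is a consequence of both the arm and the pain score. Holding it fixed compares patients on dexamethasone with controls who happened to take the same amount of opioid, and these are no longer groups formed by chance.

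The distortion can go either way. If patients in more pain take more narcotic, adjustment removes part of a real benefit. If narcotic intake mainly shows up as lower pain, adjustment exaggerates the benefit.

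The plan also leaves open whether narcotic use enters as a patient total or interval by interval. With two unranked analyses of one primary endpoint, the t test and the model can disagree, and the choice between them could be made after the results are known.

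**Working it through.** **1. The plan's own figure.** Inputs from section 10(i): 30 per arm, difference 1.5, SD 2.0, two-sided 0.05.

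- Standard error = 2.0 × √(2/30) = 0.516
- 1.5 / 0.516 = 2.90
- Exact power (noncentral t, 58 df) = 81.5%

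The stated 81% reproduces for the unadjusted t test.

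**2. One value per patient, adjusted for narcotic use.** Two further inputs are needed, and the documents give neither, so both are assumptions: *d*, the reduction in narcotic use in within-arm SDs, and *r*, the within-arm correlation of pain with narcotic use. Negative differences favour dexamethasone.

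- Adjusted difference = true difference + r × 2.0 × d
- Standard error = 2.0 × √(1 − r²) × √(2/30) × √(1 + d²/4), with 57 df

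Example with d = 0.75, r = 0.5, true difference −1.5:

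- Adjusted difference = −1.5 + 0.5 × 2.0 × 0.75 = −0.75
- Standard error = 2.0 × 0.866 × 0.258 × 1.068 = 0.478
- Ratio = 1.57, power 34%

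Results for d = 0.75:

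| r | True difference −1.5: adjusted difference (power) | No true difference: adjusted difference (rejection at nominal 5%) |
|---|---|---|
| −0.3 | −1.95 (95%) | −0.45 (13%) |
| 0 | −1.50 (76%) | 0 (5%) |
| 0.3 | −1.05 (50%) | +0.45 (13%) |
| 0.5 | −0.75 (34%) | +0.75 (34%) |
| 0.7 | −0.45 (20%) | +1.05 (75%) |

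At r = 0.5, d = 0.5 gives −1.00 (57%) and d = 1.0 gives −0.50 (17%). Simulation of 40,000 trials per cell agrees to about one percentage point. At the design effect the expected sign reverses only if r × d exceeds 0.75. The largest product used here is 0.7 × 0.75 = 0.525, so it does not reverse in these scenarios.

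**3. Repeated scores, three ways of coding narcotic use.** A random-intercept mixed model was simulated with 30 per arm and 3,000 trials per cell. The assumptions are:

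- six 4-hourly scores, control mean 5, within-patient SD 1.5;
- Percocet by the section 10(g) bands, taken every time or half the time;
- each tablet lowering the next score by 0, 1 or 2 points.

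The model was tuned so that the unadjusted difference is about −1.5, the SD of average VAS is 2 and unadjusted power is 80–81%.

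| Narcotic use entered as | Tablets always taken | Tablets taken half the time |
|---|---|---|
| Patient total | −0.08 to −0.10 (power 7–10%) | −0.65 to −0.67 (40–42%) |
| Tablets in the same interval | −0.38 to −0.44 (57–67%) | −1.23 to −1.31 (77–80%) |

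Entered as tablets in the previous interval, the result is −1.49 to −2.02 (80–81%) across both patterns of use. Within-arm correlation of average VAS with total tablets came out at 0.97 when tablets were always taken and 0.70–0.76 when half were taken. The same underlying trial therefore reports quite different treatment effects depending on a coding choice that the plan does not state.

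**The case against.** The strongest reply is that a hierarchy can be inferred. The endpoint in section 10(f) is one average VAS per patient, the t test is named first for the endpoints, and the only VAS power calculation uses it. The mixed model could then be a supplement on pain over time. This is a reasonable reading and the t test is sound, but the plan never says so, and it presents the mixed model simply as the analysis between the two groups.

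A second reply is that rescue opioid can mask a block effect, so pain in the absence of rescue is a legitimate target, and not every departure from −1.5 is an error. That stands as a reason for a supportive analysis. However, the plan states no such target, and entering total opioid use as a covariate does not deliver it.

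Several limits on the figures also stand.

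- Power is not always lost. Previous-interval coding keeps 80–81%.
- The −0.08 end needs every banded tablet to be taken, which makes the covariate almost a copy of the outcome.
- The simulation leaves out morphine and uses six scores. The planned mean stays of 16 and 18 hours in section 10(i) suggest about four. A four-score run of the patient-total model gave −0.14 (always taken) and −0.78 (half taken), so the pattern remains.
- The sentence on adjusting the pain score may only restate the covariate control. It is ambiguous.
- The documents list two primary endpoints without calling them co-primary or saying whether both must succeed. The argument needs only that narcotic use is a post-randomisation outcome.

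**Conclusion.** The concern holds, and the plan must be changed before analysis. As written, one of its two pain analyses conditions on a primary endpoint affected by treatment, and nothing prevents that analysis from being the one reported. This is an error in the analysis and not just a missing detail.

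The t test is unaffected and keeps its 81% power. That figure cannot be assumed for the medication-adjusted model. The size and direction of the distortion depend on r, the narcotic reduction, prn behaviour and the coding of narcotic use, none of which the documents give. The computed results are therefore illustrations, not predictions. That the adjusted model does not estimate the total effect of dexamethasone on pain follows from the protocol's own text and does not depend on those values.

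**What to change.** In section 10(i):

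1. Name one primary VAS analysis with no post-randomisation covariate. It can be the t test on average VAS, or a mixed model with arm, time and arm-by-time.
2. Remove narcotic use as a covariate from that analysis, and delete the undefined adjustment of pain scores.
3. Analyse narcotic use as a primary endpoint in its own right.
4. If unequal rescue use is a concern, pre-specify either a medication-adjusted model, stating how narcotic use is coded, or a joint pain-and-opioid measure. Label it supportive or exploratory.

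The cost is wording only, with no new data and no additional patients. If the t test is named, the 81% power stands as calculated. If the mixed model is named, the power statement should be matched to it.

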### 6) Background

## Enhanced pain control after reduction mammoplasty with bupivacaine and dexamethasone regional block

Breast reduction is among the most common procedures performed by the Plastic Surgery division at Temple University Hospital. These patients are generally admitted for 23 hour observation primarily due to significant postoperative pain. Currently regional nerve block is routinely performed with bupivacaine infiltration. This provides effective immediate postoperative pain control but is limited by the 2 to 8 hour duration of action provided by this drug. These patients typically require significant amount of narcotic analgesia in the postoperative period. Exparel® (bupivacaine liposome injection) is a commercially available long acting formulation of bupivacaine however its significant cost has been deemed prohibitively high for use at this and most other institutions.

A number of studies in the anesthesia literature have demonstrated that addition of dexamethasone to bupivacaine when administered as a perineural block extends the duration of analgesia. In Bjorn, et al. (Reg Anesth Pain Med, 2016 Dec) saphenous nerve block with 10mL 0.5% bupivacaine + 1mL 0.4% dexamethasone after ankle surgery significantly extended the time to first narcotic request compared to control with bupivacaine alone. Maher, et al. (Pain Med, 2016 Jul) examine the use of both IV dexamethasone (8mg) and combination perineural dexamethasone and bupivacaine as intercostal nerve block during VATS. They demonstrate statistically significant decrease in pain at 8, 20, and 24 hours postoperatively. Other studies have obtained similar results in a variety of orthopedic and neurosurgical procedures.

A PubMed search using terms “dexamethasone” and “nerve block” did not return any studies that pertain to plastic reconstructive surgeries including but not limited to breast reduction. Additionally, searches using “breast reduction” and “nerve block” or “mammoplasty” and “nerve block” returned only 1 relevant study that examines the use of Exparel® nerve block during mastectomy (Abdelsattar 2016). Again, no studies examine methods of prolonging the duration of regional anesthesia after reduction mammoplasty

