### **e) Study Timelines**

- Data collection will occur over a period of 12 months
- [Interim analysis will be conducted by an independent at 6 months to confirm the quality of the data](#)
- Patient participation is limited to the length of the hospitalization for breast reduction procedure plus the first postoperative visit. For most subjects this will be 24 hours as inpatients with the postoperative visit occurring 1 week after surgery.

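### Length of stay is tested in hours without adjustment although discharge is expected to follow the clock; adjusting for time of day of surgery could recover some precision

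*Combined protocol and SAP*

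**What the plan says.** Section 10(f) makes length of stay a secondary endpoint: "Secondary endpoints are need for antiemetic therapy, length of hospitalization". Section 10(i) describes the expected pattern in clock terms: "The difference is generally expected to be between a “before lunch” or “after lunch” discharge on post-operative day 1". The analysis follows directly: "A two-group t test with a 0.05 two-sided significance level will be used to evaluate a difference in length of hospital stay". The planning figures are given as "assuming group A mean hospital stay of 16 hours and group B mean stay of 18 hours with 4 hour standard deviation", from which the plan concludes that "a sample size of 63 is required to achieve 80% power with" p < 0.05.

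No section says which timestamp starts the stay (admission, start of surgery or end of surgery) or which one ends it. The only covariates that Section 10(i) mentions are vital signs and pain medication, and both belong to the pain-score model. Nothing adjusts length of stay for time of surgery.

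Two other sections give a usual stay. Section 6 says "These patients are generally admitted for 23 hour observation primarily due to significant postoperative pain", and Section 10(e) says "For most subjects this will be 24 hours as inpatients with the postoperative visit occurring 1 week after surgery".

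**The concern.** Elapsed stay is discharge time minus start time. If patients leave in one of two windows around midday on the day after surgery, discharge time varies little and the operating list largely sets the start. The spread of start times then passes into the endpoint.

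An illustration, with the stay counted from end of surgery: two patients both leave at 11:00 on day 1. One operation ended at 11:00 the day before and the other at 18:00. Their stays are 24 h and 17 h. The 7 h gap owes nothing to the block and is larger than the 2 h effect the plan looks for.

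An unadjusted t test leaves this variation in the error term, although surgery times should be easy to obtain because Epic is already the data source. At stake is the chance of detecting a real shift in discharge on a secondary endpoint that the plan powers separately.

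**Working it through.** **Inputs from the plan.** Difference 18 − 16 = 2 h, SD 4 h, two-sided 0.05, 80% power (Section 10(i)); 1:1 allocation (Section 10(g)); 30 per arm (Section 10(i)), about 60 in total (Section 10(d)).

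**Step 1: reproduce the plan's figure.** n per arm = 2 × (1.96 + 0.84)² × (4/2)² = 62.8, so 63. The stated 63 is therefore a per-arm number (63.8 by the exact t calculation). With 30 per arm the standardised effect is 2/4 = 0.5 and the power of the t test is 47.8%.

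**Step 2: is there bias?** Stay = D − S, where D is discharge time and S is start time. Allocation is random, so S has the same expected value in both arms and cancels from the expected difference. Simulated t tests (20,000 runs per setting, 30 per arm, a true 2 h shift between two discharge windows, surgery end times spread over 0 to 12 h) gave mean differences between 1.99 and 2.01 h. Only precision changes.

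**Step 3: is 4 h wide for a before/after-lunch contrast?** Suppose discharge takes one of two times g hours apart and the 2 h shift comes from patients moving between them. The proportions are then 0.5 ± 1/g and the within-arm variance is g²p(1 − p). The gap g is an assumption.

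| g (h) | Discharge SD (h) | Share of the 16 h² variance from elsewhere |
|---|---|---|
| 3 | 1.1 | 92% |
| 4 | 1.7 | 81% |
| 6 | 2.8 | 50% |

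The remainder could be start time, unusually long stays or a cautious planning figure. The documents do not say which.

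**Step 4: what adjustment could recover.** Let surgery timing contribute an SD of s to the 4 h, with discharge time independent of surgery time. Adjusting leaves a residual SD of √(16 − s²). The values of s are assumptions.

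| s (h) | Share of variance, s²/16 | Residual SD (h) | Power, 30 per arm |
|---|---|---|---|
| 0 | 0% | 4.00 | 48% |
| 1.5 | 14% | 3.71 | 54% |
| 2 | 25% | 3.46 | 59% |
| 2.5 | 39% | 3.12 | 68% |
| 3 | 56% | 2.65 | 82% |

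For scale, end times spread evenly over W hours have an SD of W/√12. Windows of 4, 6, 8 and 10 h account for 8%, 19%, 33% and 52% of the 16 h² variance.

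**Step 5: if later surgery delays discharge.** Let discharge move b hours for each hour of later surgery. Surgery timing with SD s then contributes (1 − b)s to the stay. With s = 3 h and b = 0.5 the contribution is 1.5 h, so adjusted power is 54% and not 82%. With s = 2 h and b = 0.5 it is 1 h, and power is 50%.

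**The case against.** The strongest reply is that hours compared by t test is a conventional choice, the comparison is randomised, and the planning SD of 4 h may already include variation in surgery time. If so, 63 per arm already allows for it and adjustment is only an efficiency preference of unknown size. The endpoint is also secondary, and Section 10(i) itself expects stays to be similar. All of this stands, and it limits the point to a modest one. It does not remove the case for a covariate that is cheap to obtain.

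A reader might infer more, and the documents do not support it:

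- *That hours of stay mainly measure when surgery ended.* The documents contain no surgery times and never say that the stay is counted from end of surgery. In the Step 4 range, surgery timing exceeds half the variance in only one of the four scenarios.
- *That the measure hides the treatment effect.* The expected 2 h difference is preserved.
- *That 16–18 h, 23 h and 24 h can be reconciled only by different start points.* The 23-hour figure can be read as an admission category, the 24 h as a rounded figure for most subjects, and 16 and 18 h are planning assumptions. Loose figures explain the gap equally well.
- *That discharge clock time would be the better endpoint.* Its variance from surgery timing is b²s², against (1 − b)²s² for hours of stay, so it is noisier whenever b exceeds 0.5. It would also replace the endpoint named in Section 10(f).

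**Conclusion.** The point holds as a minor loss of precision on a secondary endpoint. The plan's own description ties discharge to the clock, yet the test leaves variation in time of surgery in the error term. Under assumed surgery-timing SDs of 1.5 to 3 h within the planned 4 h, adjustment would lift power at 30 per arm from 48% to between 54% and 82%. These figures assume that discharge time does not depend on surgery time, and the gain shrinks to the extent that it does. The true size cannot be worked out from the documents. There is no bias, and no primary conclusion depends on it.

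The 48% starting value should not be blamed on the choice of measure. It arises because 63 per arm is needed and about 60 in total are planned. That is a separate issue.

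**What to change.** In Section 10(i), keep length of hospital stay as the secondary endpoint. Name one Epic timestamp as its start and recorded discharge as its end. Replace the unadjusted t test for this endpoint with a linear model (ANCOVA) of hours on treatment group and time of day of surgery. State in advance whether start or end of surgery is used, and take it from Epic. The model estimates the slope, which is b − 1 in the notation of the working, so it adapts whether or not later surgery delays discharge. When stating the start of the stay, say how the 16 and 18 h assumptions relate to the stays in Sections 6 and 10(e). Do not replace the endpoint with discharge clock time.

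The cost is a change of analysis wording, one extra timestamp in the Epic extraction and one degree of freedom (57 residual instead of 58 with 60 patients). No patients or procedures are added. If surgery timing explains nothing, the loss is negligible.
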